## **5 Study Design**

Prospective, post-market, hypothesis generating, pilot study

### **5.1 Scale and Duration**

A total of 50 subjects, 25 undergoing 2D laparoscopic surgery and 25 undergoing 3D laparoscopic surgery, will be enrolled and treated at 1 study site in Canada. Each subject will be followed for approximately 30 days following the study procedure. It is anticipated for the entire study to last 9 months.

### **5.2 Treatment Assignment**

A total of 50 laparoscopic roux-en-y gastric bypass surgeries will be assessed as part of this study. Twenty-five consecutive 2D laparoscopic surgeries and 25 consecutive 3D laparoscopic surgeries.

### **5.3 Justification for the Study Design**

This study was designed as a pilot study to compare the impact of 2D versus 3D visualization on surgical performance, as measured by the OR BlackBox® Platform, during laparoscopic bariatric surgery. Data from this study will be used to potentially generate a hypothesis for a larger, pivotal study.

## **6 Subject Selection**

### **6.1 Study Population and Eligibility**

Patients who meet all of the inclusion criteria and none of the exclusion criteria will be considered for enrollment in this study.

### **6.2 Inclusion Criteria**

1. ≥ 18 years of age
2. Scheduled to undergo elective, primary roux-en-y gastric bypass surgery
3. BMI of 35 to 54.9
4. Willing and able to provide informed consent

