**6.3 Exclusion Criteria**

1. Previous open abdominal surgery
2. Previous open or laparoscopic upper GI surgery
3. Contraindicated for laparoscopic bariatric surgery
4. Unable or unwilling to provide informed consent

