# 9 Visit Schedule

## 9.1 Screening/Baseline (Clinic Visit)

- Eligibility criteria
- Informed consent
- Demographics
  - Age
  - Gender
  - BMI
- Medical history
  - Alcohol use
  - Tobacco use
  - Co-morbidities
  - Previous surgeries (ensure previous surgeries do not meet exclusion criteria)

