#### **11.4 Statistical Methods**

Descriptive analysis of data will be performed using the Student's *t*-test and Chi-square test. Association of numerical variables will be performed using Parson's correlation. For determination of whether the 2D or 3D monitor is correlated with intraoperative errors or other factors, binary logistic regressional models will be used.

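### Section 11.4 compares two non-randomised series of 25 cases without naming a covariate, although BMI is already collected and could be adjusted for at almost no cost

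*Combined protocol and SAP*

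**What the plan says.** Section 5.2 sets the assignment: "Twenty-five consecutive 2D laparoscopic surgeries and 25 consecutive 3D laparoscopic surgeries". Section 11.3 repeats it. Neither mentions randomisation, stratification or matching, and the order of the two series is not given.

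Section 6.2 admits a "BMI of 35 to 54.9". Section 6.3 narrows the case mix by excluding "Previous open abdominal surgery" and "Previous open or laparoscopic upper GI surgery". Section 9.1 records BMI under demographics, with age and gender, and records previous surgeries under medical history. Only the previous-surgeries entry carries a reminder to check eligibility.

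On analysis, Section 11.4 states: "Descriptive analysis of data will be performed using the Student's" *t*-test and the chi-square test. It adds correlation of numerical variables. To relate the 2D or 3D monitor to intraoperative errors or other factors, "binary logistic regressional models will be used". No covariate is named for any of these. Section 11.2 says that no hypothesis is tested, while Section 5.3 gives the purpose as comparing 2D with 3D, with a possible hypothesis for a pivotal study to follow.

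**The concern.** In a non-randomised comparison nothing in the design makes the arms alike in the features that make an operation harder. BMI is an obvious candidate in bariatric surgery, the eligible range is wide, and the value will be in the database. An unadjusted comparison carries any BMI difference between the series into OSATS, GERT errors, procedure time and workload, in proportion to how strongly BMI is related to each.

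At stake is the direction and size of the signal taken forward. A pilot of this kind is read for its point estimates. With 25 per arm, a shift of one or two tenths of an SD cannot be told apart from a real effect of visualisation. Leaving the adjustment unspecified also lets covariates be chosen after the results are seen.

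**Working it through.** The plan gives no sample-size, power or precision figure to reproduce; 25 + 25 is simply declared (Section 11.3).

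**Inputs from the protocol.** n = 25 per arm (Section 5.1). BMI window 54.9 − 35 = 19.9 units (Section 6.2).

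**Assumed inputs, not in the documents.** BMI SD 4 to 5.74, the upper value being a uniform spread over the window, 19.9/√12 = 5.74. BMI–outcome correlation r of 0.3 to 0.5. Two-sided 5% level.

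**1. Chance difference in mean BMI.** SE = SD × √(2/25).
- SD 4: SE 1.13; 95% range ±2.2 units; a gap above 2 units in about 8% of studies.
- SD 5.74: SE 1.62; 95% range ±3.2 units; a gap above 2 units in about 22% of studies.

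**2. Shift in the comparison from a 2-unit gap.** Shift in outcome SD = (2/SD) × r.
- SD 5.74: 0.348 × 0.3 = 0.10, up to 0.348 × 0.5 = 0.17.
- SD 4: 0.5 × 0.3 = 0.15, up to 0.5 × 0.5 = 0.25.

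The two ranges run in opposite directions. The 0.25 shift needs SD 4, where a 2-unit gap arises by chance in only 8% of studies; where the gap is more common (22%), the shift is 0.10 to 0.17. Against the standard error of the comparison, √(2/25) = 0.28 SD, the shift is 0.10/0.28 ≈ 0.4 to 0.25/0.28 ≈ 0.9 of one standard error.

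**3. Error rate with no true 2D/3D effect.** Simulation of a continuous outcome, BMI SD 5, 10,000 runs per scenario:

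| Systematic BMI shift | Unadjusted rejection, r = 0.3 / 0.5 | BMI-adjusted rejection, r = 0.3 / 0.5 |
|---|---|---|
| 0 units | 5.2% / 5.5% | 5.1% / 5.2% |
| 2 units | 6.9% / 11.0% | 5.1% / 5.0% |
| 3 units | 9.5% / 18.1% | 4.9% / 5.1% |
| 4 units | 13.5% / 27.8% | 4.8% / 5.0% |

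At 3 units the spurious difference is 0.18 to 0.30 SD unadjusted and about zero adjusted.

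**4. Precision.** With BMI balanced, adjustment multiplies the interval width by √(1 − r²): 0.954 at r = 0.3 and 0.866 at r = 0.5. With a 2-unit gap, BMI overlaps with arm and the variance rises by a factor of about 1 + (2/SD)²/4, that is 1.03 (SD 5.74) to 1.06 (SD 4). The net width is 0.954 × √1.03 ≈ 0.97 to 0.954 × √1.06 ≈ 0.98 at r = 0.3, and 0.866 × √1.03 ≈ 0.88 to 0.866 × √1.06 ≈ 0.89 at r = 0.5. The narrowing is then about 2–3% or 11–12%.

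Steps 2 to 4 apply to continuous outcomes. The precision gain does not carry over to odds ratios from a logistic model.

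**The case against.** The strongest defence is the context. There is no primary endpoint, no hypothesis is tested, and Section 11.4 calls its t-tests descriptive. Chance imbalance is already covered by the sampling error of the t-test, as the zero-shift row shows. A systematic BMI difference would need a cause, and the documents suggest none: one site, one set of criteria, elective primary bypass only, eight months of enrolment. All of this stands, and it makes the point an improvement to the analysis rather than a flaw that undoes the study. It does not remove it. Section 5.3 makes the 2D/3D comparison the purpose, and a gap that has arisen, by chance or not, still displaces the estimate in hand.

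Several stronger readings are tempting and are not supported:
- A reader might infer that the BMI criterion is at fault. It is not; the gap lies in Section 11.4, and eligibility need not change.
- A reader might infer that the plan excludes BMI from analysis or collects it only to check eligibility. Section 9.1 lists it as a demographic variable, and the planned correlations could include it. Adjustment is unspecified, not ruled out.
- A reader might give earlier laparoscopic surgery outside the upper GI tract equal weight as a source of difficulty. The documents give no frequency or effect for it.
- A reader might infer that the clinic BMI is out of date by surgery and that a further weight is needed. Nothing in the documents indicates a change.

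**Conclusion.** The point holds as an unspecified adjustment in Section 11.4. Two non-randomised series are to be compared without a named covariate while a plausible one is already recorded. Under the assumed SD and correlation, a 2-unit BMI difference would move the comparison by about 0.10 to 0.25 outcome SD, less than one standard error. The error rate rises only if the series differ systematically, and the documents neither show nor exclude that. The sizes are illustrations, because the protocol gives no BMI spread and no BMI–outcome correlation. The case for change rests on the low cost and on the use of the estimates to shape a pivotal study, not on demonstrated bias.

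**What to change.** In Section 11.4, pre-specify baseline BMI (continuous) as a covariate in the 2D/3D regression models for OSATS, GERT errors, procedure time and NASA-TLX. The continuous outcomes will need linear models, since Section 11.4 now gives them only t-tests and correlation. Report the adjusted results next to the unadjusted ones.

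Under Section 9.2 each surgical team member completes the NASA-TLX, so one operation yields several scores. Either average them per case or include a random effect for operation.

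Tabulate BMI, age, gender and previous laparoscopic surgery by arm.

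The cost is wording in the plan and one model degree of freedom in 50 cases; no patients, visits or new data are needed. The limit is that BMI adjustment deals with one measured difference. It does not remove confounding by calendar time, by learning, or by operator (for example, which fellow performs the jejunojejunostomy), and the report should say so to avoid false reassurance.

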**6.3 Exclusion Criteria**

1. Previous open abdominal surgery
2. Previous open or laparoscopic upper GI surgery
3. Contraindicated for laparoscopic bariatric surgery
4. Unable or unwilling to provide informed consent

**6.4 Recruitment of nursing, anesthesia and surgical staff**

Prior to start of the study, approval will be obtained from the clinical manager of perioperative services. Nursing staff as well as a technical assistant will be identified through the roster and addressed by the clinical Leader Managers of Perioperative Services, via their St Michaels. Nursing staff as well as a technical coordinator will then obtain written informed consent.

Occasionally, anesthesia residents will be scheduled for the unit's OR. After approval by the anesthesiology program director, anesthesiology residents will be contacted and informed of the study.

[name] as well as the participating staff surgeon in the Department of General Surgery at St Michael's Hospital will be study subjects in the observed procedures, and will also sign the written informed consent prior to the procedure. Fellows will be informed of the study prior to their rotation. Surgical residents who are undergoing 2 or 3 month rotations will be contacted by the General Surgery Program director, and then approached by the research coordinator, and the informed consent will be obtained.

Since all OR team members including nursing, anesthesia and surgical team will be recorded, they are all required to provide the informed consent. However it should be clarified that only the surgical team will be evaluated.

**7 Subject Accountability****7.1 Point of Enrollment**

A subject will be considered enrolled in the study if they meet all eligibility criteria specified in Section 6 of this protocol and after the subject signs and dates the Research Ethics Committee (REC) approved informed consent form (ICF). No study-related procedures can take place until the ICF is signed.

**7.2 Withdrawal**

All subjects enrolled in the clinical study (including those withdrawn from the clinical study or lost to follow-up) shall be accounted for and documented. If a subject withdraws from the clinical study, the reason(s) shall be reported. Reasons for withdrawal include:

- Physician discretion

- Subject choice to withdraw consent
- Lost to follow-up
- If the subject dies due to any cause
- Termination of the study by Sponsor, IRB/EC or regulatory authority

The reason for a subject's failure to return for the necessary follow-up visits or for a subject's discontinuance from the study must be determined and recorded in the Case Report Forms (CRFs).

All applicable CRFs up to the point of subject withdrawal must be completed. Subjects who are lost to follow-up should have documented attempts to contact them prior to being deemed lost.

Additional data may no longer be collected after the point at which a subject has been withdrawn from the study or withdraws his/her consent, for whatever reason. Data collected up to the point of subject withdrawal may be used for study analysis.

### **7.3 Enrollment Controls**

Enrollment figures will be regularly communicated to Olympus. Enrollment should not exceed 50 subjects as specified in Section 5.1 of this protocol.

## **8 Study Methods**

### **8.1 Data Collection**

The schedule of data collection is illustrated in Table 1.

## 8.2 Informed Consent

All subjects taking part in this clinical study must undergo the informed consent process. Subjects must be allowed adequate time to review the consent, raise questions, and make a voluntary decision to participate in the clinical study. Each subject must sign and date the REC approved ICF before any clinical study-related procedures are performed. A copy of signed ICF will be provided to the subject for his/her records. A subject's participation in the clinical study begins with the signing and dating of the ICF.

# 9 Visit Schedule

## 9.1 Screening/Baseline (Clinic Visit)

- Eligibility criteria
- Informed consent
- Demographics
  - Age
  - Gender
  - BMI
- Medical history
  - Alcohol use
  - Tobacco use
  - Co-morbidities
  - Previous surgeries (ensure previous surgeries do not meet exclusion criteria)

## 9.2 Procedure (Hospital Visit)

- Laparoscopic 2D or 3D roux-en-y gastric bypass surgery
  - All study procedures will be video and audio recorded using 2 mounted cameras and auxilliary microphones. One camera will be focused on the surgical field and the second focusing on the OR door.
  - The laparoscopic video (internal subject view) will be recorded according to standard of practice.
  - All video and audio recordings will begin after the subject has been intubated and will end at skin closure prior to extubation.
- Procedure time (minutes) (skin-to-skin)
  - The Principal Investigator will perform the gastrojejunostomy (GJ) anastomosis
  - A surgical fellow will perform the jejunojejunostomy (JJ) anastomosis
- Adverse events (Including Clavien Classification of Surgical Complications (CCSC))
- Device deficiencies
- STAR Questionnaire will be completed by each surgical team member within 24 hours of surgical procedure

**Table 1: Data Collection Schedule**

Procedure/Assessment	Screening/Baseline (Clinic Visit)	Procedure (Hospital Visit)	Post-Procedure OSATS and GERT	30 Day Follow-up  (Telephone Call)	Follow-up Visits
Visit Window	N/A	N/A	Within 30 Days After the Procedure	+/- 10 Days	Unscheduled Visit  (Clinic Visit)
Eligibility Criteria	X				N/A
Informed Consent Form	X				
Demographics	X				
Medical History	X				
Laparoscopic 2D or 3D Roux-en-Y Gastric Bypass Surgery		X			
STAR Questionnaire (Immediately following procedure in OR)		X 			
NASA Task Load Index		X			
Visualization and Physical Symptoms Questionnaire		X			
Surgical Team Demographic Questionnaire		X			
ESA: Video Feed Review (Completion of OSATS & GERT Tools)			X 		
Device Deficiencies			X		
Adverse Events		X	X		

 Immediately following the procedure, the STAR Questionnaire will be completed by each member of the OR team who participated in or attended the surgical procedure.

 Post-Procedure is not a subject follow-up visit, it is the point at which the video and audio feed of each surgical procedure will be reviewed by an ESA to complete the OSATS and GERT tools.

 Unscheduled Visits for subjects may be performed between protocol specified visits as deemed appropriate by the Investigator.

 End of study will be reached after completion of the 30 Day Follow-up Telephone Call, subject withdrawal, or lost to follow-up, whichever occurs first.

- Only the role of the surgical team member will be captured on this form, no names.
- NASA Task Load Index will be completed by each surgical team member within 24 hours of surgical procedure
- Visualization and Physical Symptoms Questionnaire will be completed by each surgical team member within 24 hours of surgical procedure
- Surgical Team Demographic Questionnaire

#### **9.3 Post-Procedure (Within 30 Days of Surgical Procedure – No Subject Follow-up)**

- Two ESAs will perform surgical video and audio review and completion of OSATS and GERT
  - ESAs are surgeons in the Investigator's research group with comprehensive knowledge OF SURGICAL PERFORMANCE ASSESSMENT as well as formal training and experience using the tools utilized in this study.
  - ESAs will not have access to the OR during study surgical procedures to ensure unbiased completion of OSATS and GERT.
- ESA 1 will review the video and audio recordings for all subjects
- ESA 2 will review the video and audio recordings for 20% of subjects to ensure objectivity during analysis. Cases for review will be randomly selected

#### **9.4 30 Day Post Procedure Follow-up (Telephone Call) (+/- 10 Days)**

- Adverse events (Including CCSC)

#### **9.5 Unscheduled Visit**

Unscheduled visits may be performed between visits required by the protocol as deemed necessary by the Investigator. Unscheduled visits will be captured on the adverse event (AE) CRF.

#### **9.6 End of Study**

End of study will be reached after completion of the 30 Day Post Procedure Follow-up Telephone Call, subject withdrawal ,or lost to follow-up, whichever occurs first.

### **10 Video and Audio Recordings**

All data records, documentation or information containing patient data will be de-identified with study numbers to ensure that persons outside of the study will not be able to identify the participating patients. The code will be kept on a password protected hard drive that will only be accessible to the Research Coordinator. The researchers will however be given access to the data sheets as required to enter additional information such as follow-up data. The video recordings will only capture the details of the operative procedures while patients will be

protected from the camera view by sterile drapes. All staff participants will be wearing surgical hoods and masks as per standard operating procedure and OR hygiene regulations.

Recorded, de-identified video files will be retained until completion of patient follow-up (30 days). If a complication occurs within this follow-up period, the material will undergo a second review by the same team of observers as in the first review. First and second review will then be compared. After 30 days the video and audio files will be permanently and securely deleted.

### **10.1 Educational Library**

Educational library is a collection of anonymized and de-identified video materials created for the purpose of future education and training of the operating room team members.

The educational video material will be created using video editing software and will contain laparoscopic and panoramic video clips where necessary. All video material will be completely anonymized. Additional video and audio filters will be applied in order to ensure full identity protection of all persons appearing in the recorded materials. Processed educational clips will be rendered completely anonymous by combining video blurring and voice altering technology.

Educational video materials will be available to Operating Room Black Box (ORBB) team members only and will be stored on a secure server as per standard protocol. The materials may be used inside of the St. Michael's Hospital for educational and training purposes only. The responsible custodian of the video materials will be the PI.

## **11 Statistical Considerations**

### **11.1 Endpoints**

#### **11.1.1 Primary Endpoint**

There is no primary endpoint for this study as it is a hypothesis generating pilot study. This study will quantify operative performance and intraoperative errors after the introduction of the 2D and 3D technology using the following tools:

- Generic Error Rating Tool (GERT)
- Objective Structured Assessment of Technical Skill (OSATS)

#### **11.1.2 Secondary Endpoints**

1. Clinically significant adverse events related to the device(s) and/or procedure.
  - Clinically significant is defined as any deviation from the normal surgical or post operative course that requires special treatment or action.

2. Operating room (OR) team's perception of human factors and teamwork following each procedure using the Modified Surgical Team Assessment Record (STAR) questionnaire.
3. NASA Task Load Index to assess mental workload and frustration
4. Visualization and Physical Symptoms Questionnaire
5. Surgical Team Demographic Questionnaire

#### **11.2 Hypotheses**

N/A – This is a hypothesis generating pilot study. As a result no statistical hypothesis will be tested as part of this study.

#### **11.3 Sample Size**

This is a hypothesis generating pilot study. As a result a sample size calculation is not required.

Fifty roux-en-y gastric bypass surgeries will be performed as part of this study; 25 consecutive surgeries will be performed using a 2D laparoscopic camera and 25 consecutive cases will be performed using a 3D laparoscopic camera.

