### 2.2 Olympus HD 3D Laparoscopic Surgical Video System

The Olympus HD 3D Laparoscopic Surgical Video System is cleared for use in Canada within the thoracic and abdominal cavities including female reproductive organs and is comprised of the following components:

- CV-190 Processor
- CLV-190 Light Source
- 3DV-190 3D Visualization Unit
- LMD-2451MT/2G4 sonly 24" 3D Monitor
- IMH-20 Image Capture System
- UHI-4 Insufflator
- K10021611 Cart
- OL-0015-08 Tall Rollstand
- LTF-190-10-3D ENDOEYE FLEX 3D Videoscope
- 3D Glasses (Regular and Clip-on Styles)

The Olympus HD 2D and 3D Imaging System is lightweight and ergonomically designed with the intention to lessen surgeon fatigue and maximize ease of use. The ENDOEYE FLEX 3D Videoscope allows for 100° of articulation in all directions while maintaining a level visual horizon regardless of viewing angle. Additionally, the system allows for focus free visualization with the ability to toggle back and forth between 2D and 3D imaging.

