## **3 Study Objectives**

This is a hypothesis generating pilot study to compare the impact of 2D versus 3D visualization on surgical performance, as measured by the OR BlackBox® platform, during laparoscopic bariatric surgery.

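### Cases are assigned only as two consecutive series of 25 with no order or overlap stated, so on the natural reading a period effect cannot be separated from the 2D/3D effect

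*Combined protocol and SAP*

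**What the plan says.** Section 5.2 (Treatment Assignment) gives the whole assignment rule: "Twenty-five consecutive 2D laparoscopic surgeries and 25 consecutive 3D laparoscopic surgeries". Section 11.3 and the synopsis repeat it: "25 consecutive surgeries will be performed using a 2D laparoscopic camera and 25 consecutive cases will be performed using a 3D laparoscopic camera". No section says which series comes first, whether the two overlap in time, or what decides a given patient's arm. The only random selection in the protocol is in Section 9.3, and it concerns which cases the second rater reviews.

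The aim in Section 3 is "to compare the impact of 2D versus 3D visualization on surgical performance". Section 5.3 adds: "Data from this study will be used to potentially generate a hypothesis for a larger, pivotal study". Section 11.2 says that "no statistical hypothesis will be tested as part of this study". Section 11.4 nevertheless names a t-test and a chi-square test, and continues: "For determination of whether the 2D or 3D monitor is correlated with intraoperative errors or other factors, binary logistic regressional models will be used". It names no term for case order or period.

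The synopsis plans eight months of enrolment. Under Section 9.2 the Principal Investigator performs the gastrojejunostomy in every case, and "A surgical fellow will perform the jejunojejunostomy (JJ) anastomosis".

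**The concern.** Two consecutive series at one site most naturally mean that one mode is used until 25 cases are done and the other mode follows. Every 2D case then belongs to one period and every 3D case to another. Anything that changes over those months and affects both modes alike (team experience, staffing, theatre routine) would appear as a difference between 2D and 3D.

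The other reading is that the two modes run side by side and that cases are unselected within each. That avoids the overlap of arm with period, but the rule that sends a patient to one mode or the other is then missing.

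What is at stake is the one comparison the study exists to make. A period effect could be read as an effect of visualization and carried into the design of the larger study.

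**Working it through.** **Inputs from the documents.** 25 + 25 = 50 cases, one site (Sections 5.1, 5.2, 11.3); eight months of enrolment (synopsis). The plan has no sample size calculation to reproduce, and the sum agrees. With even accrual (an assumption), 50/8 = 6.25 cases a month, and 25/6.25 = 4 months per series.

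**Assumptions.** Sequential series; a continuous score with unit SD; two-sided 5% t-test, 25 v 25; no true 2D/3D effect. The documents give no SD, drift or step, so ranges are shown. Simulated rates use 40,000 trials per cell.

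**1. Change at the switch.** Let arm = 1 for cases 26–50 and let step = 1 after case 25. The two columns are identical, so the design matrix [1, arm, step] has rank 2 of 3. No analysis can separate them, and a step of *s* SD biases the arm difference by exactly *s* SD. Adjusting for a linear trend does not help: with a 0.5 SD step the mean adjusted arm estimate is still 0.498 SD.

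**2. Linear trend.** The correlation of arm with case order is 0.866. The variance inflation factor is 1/(1 − 0.866²) ≈ 4.0, so the standard error doubles. The 95% CI half-widths are:
- unadjusted: t(48) × √(2/25) = 0.57 SD
- trend-adjusted, consecutive series: t(47) × √(2/25) × 2.00 = 1.14 SD
- trend-adjusted, permuted blocks: 0.57 SD (mean inflation factor 1.0001)

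**3. Unadjusted bias and rejection rate.** A linear drift of D SD from case 1 to case 50 gives bias D × 25/49. A step of *s* SD after case k (k ≤ 25) gives bias *s* × k/25.

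| Shared change (assumed) | Bias, SD | p<0.05, consecutive | p<0.05, permuted blocks |
|---|---|---|---|
| Drift 0.25 SD | 0.13 | 7% | 5% |
| Drift 0.5 SD | 0.26 | 14% | 5% |
| Drift 1 SD | 0.51 | 42% | 4% |
| 0.5 SD step after case 8 | 0.16 | 8% | 5% |
| 0.5 SD step after case 12 | 0.24 | 13% | 5% |
| 0.5 SD step after case 17 | 0.34 | 21% | 4% |
| 0.5 SD step after case 25 (worst case) | 0.50 | 41% | 4% |

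The exact noncentral t value for the last row is 0.410.

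**4. What allocation from a list does and does not do.** With permuted blocks, [1, arm, step] had rank 3 of 3 in all 2,000 lists generated. Learning specific to 3D is a different matter. If 3D cases start 0.5 or 1 SD worse and improve linearly to zero by the 25th 3D case, the mean bias is −0.25 or −0.50 SD and rejection is about 14% or 39–40% under both designs.

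**5. Practical limits of the list.** With blocks of 2 and 4 chosen with equal chance, guessing the arm with fewer cases so far is right about 72% of the time, against 50% by chance. With whole-day allocation at two cases a day (assumed), each arm's count is even, so 25:25 is impossible and the nearest split is 24:26.

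**The case against.** The strongest reply is that this is a declared choice in a pilot. The title calls it a feasibility study of the recording platform's practical utility, there is no primary endpoint, and Section 11.2 disclaims hypothesis tests. Consecutive series are a familiar pilot format. This stands as a reason for moderate severity. It does not remove the problem: bias in an estimated difference is the same whether or not a p-value is attached, the objective is comparative, and Section 11.4 names tests and a model for the 2D/3D monitor.

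Second, sequential series are inferred. That is right. What is certain is only that order, overlap and the assignment rule are undefined; the aliasing follows on the natural reading.

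Third, the magnitudes are assumed, and 41% needs a step exactly at the switch. That also stands, which is why the drift range is the fairer guide. The rates apply to a t-test on a continuous score; the logistic models in Section 11.4 were not simulated.

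Fourth, randomising leaves 3D-specific learning in the contrast and brings predictability, since the operator cannot be blind to the mode and is also the conflicted investigator described in Section 29. Both points are correct and belong in the remedy.

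Fifth, the Section 17 accountability records hold dates of use by subject, so case order can be recovered, and Section 11.4 does not exclude covariates. That helps the remedy, but it is not a plan to report or adjust by sequence.

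A reader might go further and infer that a change of fellow between series will confound the comparison. The documents do not show one: they give 2 or 3 month rotations for residents only, and the fellow performs only the jejunojejunostomy. No figure here rests on it.

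**Conclusion.** The point holds and should be fixed; it does not invalidate the study. The protocol leaves order, overlap and assignment undefined. If the series are sequential, a shared change at the switch is fully aliased with the 2D/3D effect; that result needs no assumed effect size. A smooth trend is only partly aliased: a linear one can be adjusted for, but only by assuming linearity and at four times the variance.

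The size in practice depends on assumptions that the documents cannot settle. For shared linear drift of 0.25 to 1 SD, false-positive rates run from about 7% to 42%, against 4–5% with permuted blocks. For a 0.5 SD step they run from 8–21% at the earlier times examined to 41% at worst.

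Two stronger conclusions are tempting and unsupported. One is that the protocol states that one series ends before the other begins; it does not. The other is that randomised allocation would let a difference be attributed to visualization alone; 3D-specific learning would remain.

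**What to change.** **Preferred.** Amend Sections 5.2 and 11.3, and the matching synopsis text:
- Allocate the same 50 cases 25:25 from a computer-generated list in randomly varying permuted blocks. Conceal each assignment until the patient has consented and the case is scheduled.
- If changing equipment between cases is impractical, allocate by operating day, accept approximate balance (for example 24:26), and allow for operating day in the analysis.
- Report results by case sequence and include it as a covariate for continuous scores. The Section 17 dates of use supply the order.
- State that this removes only period effects shared by both arms, and that 3D-specific learning stays in the contrast.

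**If consecutive series are kept.** State their order and dates, report by case sequence, and say that arm and period cannot be separated, so a difference must not be attributed to visualization alone.

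**Cost.** The preferred change needs an amendment and consent wording with ethics approval before implementation (Section 15), and an allocation list. It needs no extra patients or study procedures. Both systems must be available throughout enrolment, teams must switch modes, and the next assignment stays partly predictable. Sections 2.1 and 2.2 list seven components in common, and Section 2.2 says "the system allows for focus free visualization with the ability to toggle back and forth between 2D and 3D imaging". But the listed 2D system has its own scope and monitor, so the site must confirm that switching is workable. The fallback costs little beyond wording.
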